 - b. Each enrolled patient will receive supplies at study visit..
 - c. At conclusion of study, the participant randomization arm will be identified by the designated pharmacist.

J. Compliance Assessment:

1. Compliance with study drug (probiotic versus placebo) will be assessed by self-reported and provider mechanisms at monthly visits.
2. Subjects will be asked by investigators how many capsules they have missed since the last monthly visit.
3. Investigators will perform capsule count of the subject's monthly distributed study drug.
4. Investigators will provide subjects with a single aluminum tube of 30 capsules for the next monthly period.

I. Clinical Protocol:

1. Investigators will recruit study participants up to 28 weeks' gestational age.
2. Following informed patient consent, patients will be blindly randomized to either study probiotic dietary supplement or placebo per computer generated randomization table.
3. A hard-copy questionnaire/data sheet will be generated for each patient and will be labeled with patient's unique number, name and other data points that we intend to collect prospectively.
4. Subjects will be initiated on probiotic or placebo consisting of one capsule daily between 20-28 weeks' gestation and continued until delivery. Once enrolled, patients will receive a study questionnaire to complete with study investigator(s) or study coordinator(s) and a monthly supply of probiotic dietary supplement vs. placebo either at enrollment or subsequent study visit. Subjects will be instructed to store capsules away

from sun and consume 1 capsule with food every day at the same time (as determined to be the most convenient time for that patient).

5. Women diagnosed with GBS bacteriuria during the index pregnancy will be enrolled/maintained in the study, will have routine GBS cultures at 35-37 weeks for study purposes, and will receive intrapartum intravenous antibiotics for GBS prophylaxis per routine standard of care.

6. As is the current standard of care, subjects will undergo rectovaginal culture for GBS at 35-37 weeks' gestation. Any subject who tests positive will be treated with intrapartum intravenous antibiotic prophylaxis per routine GBS management protocol.

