7. Women who deliver preterm will receive chemoprophylaxis unless their GBS status within the most proximate 4 weeks is known per routine GBS management protocol. We will obtain a culture prior to initiation of antibiotics in those women delivering preterm without known group B strep status.

8. Study visits will be conducted during routine monthly prenatal appointments to assess adverse events, study treatment compliance, and to dispense subsequent 30-day supply of probiotic or placebo capsules.

Patients will complete a study visit questionnaire with the investigator(s) or study coordinator(s). Patients will also receive an additional monthly allotment of 30 capsules. The capsule bottle from the previous cycle will be collected and dated if there are capsules remaining in the bottle. Remaining capsules will be counted and refrigerated for future use.

9. Patient questionnaire/database assessing adverse events will be amended at each study visit, which will occur monthly. The questionnaire/database will assess adverse events, including rash, significant nausea/vomiting, significant diarrhea, persistent fever, and compliance data. The questionnaire will also remind patients that all adverse events must be reported to the Protocol Director immediately at all times.

10. Additionally, subjects may opt to have serial vaginal swabs collected to assess potential beneficial effects of probiotics on the vaginal microbiota and BV status. Vaginal swabs will be collected (either by study personnel or self-collected by the study participant). Swabs will be inserted 1-2 inches into the vaginal introitus and spun for 20 seconds and then withdrawn. Swabs will be collected at the following time points: prior to probiotic/placebo initiation, every 1-4 weeks from time of enrollment to time of delivery, and postpartum serially up to 12 months. These swabs will be stored at -20 degrees Celsius or colder for additional microbiologic analyses.

11. Additionally, placental tissue may be collected at time of delivery for possible future microbiome and/or other analyses.

12. Labor: The patient will receive standard delivery and newborn care. Patients with a positive GBS culture will be treated with standard antibiotics in labor.

13. Postpartum and neonatal care: The patient will receive routine postpartum care per the obstetric team. Data regarding her postpartum course and neonatal outcomes will be collected.

G. Sample size calculation:

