1. The baseline rectovaginal GBS colonization is approximately 25% in recent years in our practice, we have powered the study to identify a 40% reduction of GBS colonization to 15%. Using a two-tailed alpha of 0.05, 133 patients per arm (266 patients total) are needed to fulfill a power of 80% to detect a difference of 40% from current baseline GBS colonization of 25%.

2. Given anticipated 30% drop out/lost to follow-up and 10% preterm delivery prior to 35-37 weeks' gestation, we propose increasing our sample size by 40% to account for this subject loss. Therefore, we propose recruitment of 372 patients total (186 in each arm).

H. Statistics:

1. Analysis will be by intention to treat. Demographic data, specific information regarding the course of labor, and outcome variables will be collected on printed and numbered data sheets and entered into a relational database (Access; Microsoft Corporation, Redmond, WA). All data management and analysis will be performed using STATA version 7 software (StataCorp – College Station, TX). Descriptive statistics will be performed. All tests of significance will be 2-tailed and an alpha level of 0.05 will be used. Categorical data will be analyzed by the uncorrected χ^2 and Fisher exact test, as appropriate. Continuous data will be analyzed by the unpaired Student *t* test.

I. Data safety and monitoring plans:

1. The Protocol Director (PD) will be responsible for monitoring data collected.

2. Patient questionnaire/database assessing adverse events will be completed at each study visits, approximately every month. The questionnaire will assess adverse events, including rash, significant nausea/vomiting, significant diarrhea, persistent fevers. The questionnaire/database will also remind patients that such events must be reported to the Protocol Director immediately at all times.

3. Serious adverse events will be reported to the PD within one week. An interim analysis will be conducted to when primary outcome data is available for 150 subjects.

4. Data or events captured by the monitoring plan will be assessed monthly.

5. The following will be monitored:

- a. Side effects related to consumption of the probiotic or placebo capsules
- b. Rates of compliance

- c. GBS colonization culture results
- d. Neonatal morbidity or mortality, including but not limited to infection and duration of hospitalization

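### Capsule side effects and compliance are actively assessed only at monthly prenatal visits, with no assessment at delivery, on stopping capsules or at withdrawal

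*Protocol*

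**What the plan says.** Capsules are taken as "one capsule daily between 20-28 weeks' gestation and continued until delivery" (Protocol, Clinical Protocol, item 4).

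Side effects are solicited by questionnaire. Item 8 sets the occasion: "Study visits will be conducted during routine monthly prenatal appointments to assess adverse events, study treatment compliance". Item 9 sets the frequency: "Patient questionnaire/database assessing adverse events will be amended at each study visit, which will occur monthly". The data safety and monitoring section, item 2, gives the same schedule: "Patient questionnaire/database assessing adverse events will be completed at each study visits, approximately every month". Appendix B is titled as the form for the monthly study visits; its content is not shown.

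Compliance follows the same calendar. The Compliance Assessment section has investigators ask about missed capsules and count capsules at monthly visits. Under item 8, leftover capsules from one cycle are collected and counted at the next visit, when the next supply is given: "Patients will also receive an additional monthly allotment of 30 capsules".

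Other routes exist for some events:
- Item 9: "The questionnaire will also remind patients that all adverse events must be reported to the Protocol Director immediately at all times".
- Data safety and monitoring, item 3: serious adverse events go to the Protocol Director within one week, with no link to a visit.
- Clinical Protocol, item 13: data on the postpartum course and neonatal outcomes are collected.
- Data safety and monitoring, items 5d and 5e: neonatal and maternal morbidity are monitored. Items 5a and 5b list capsule side effects and compliance rates, without a collection time of their own.

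The sample size section expects substantial loss: "Given anticipated 30% drop out/lost to follow-up and 10% preterm delivery prior to 35-37 weeks' gestation". It gives neither cause nor timing for the 30%. The Protocol and the SAP both specify analysis by intention to treat. The SAP describes no adverse event analysis.

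**The concern.** Active assessment stops at the last monthly prenatal visit, but exposure does not. Followed exactly, the plan has no occasion on which a woman is asked about side effects between that visit and delivery, and no step at which her last tube is returned and counted. Nor is there an exit assessment for a woman who stops capsules or withdraws.

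What is at stake is how well monitored items 5a and 5b are measured. Spontaneous and solicited reports do not have the same sensitivity, so pooling them does not give a clean rate. If one arm were less well tolerated and its women left more often for that reason, some of its events would go unsolicited, and side-effect rates by arm could be biased toward equality. That is conditional on unequal tolerability, which the documents neither assert nor exclude.

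**Working it through.** **1. The plan's own figure that uses the 30%.** Sample size section: 133 per arm, 266 in total, increased by 40% (30% plus 10%). 266 × 1.40 = 372.4 and 133 × 1.40 = 186.2, which match the stated 372 and 186 after rounding. Only this inflation step is checked here.

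**2. Which events have an assessment attached.**

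| Event | Side-effect questionnaire | Capsule count | Other stated route |
|---|---|---|---|
| Monthly prenatal visit | Yes (items 8, 9) | Yes (Compliance Assessment; item 8) | – |
| Delivery or postpartum | None stated | None stated | Postpartum course, neonatal outcomes, morbidity |
| Stopping capsules | None stated at the time | None stated at the time | Next monthly visit, if she attends |
| Withdrawal or loss | None stated | None stated | Spontaneous reporting |
| Serious event, any time | – | – | Protocol Director within one week |

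**3. Length of the final interval.**

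Inputs from the Protocol: start at 20-28 weeks (days 140 to 196) and capsules to delivery (item 4); visits about monthly with 30 capsules dispensed each time (item 8). Assumed, because the documents do not give them: visits exactly every 28 or 30 days counted from the first capsule, starts spread evenly over the range, and delivery at 37 to 41 weeks.

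Gap = (delivery day − start day) modulo 28 or 30. Share = gap ÷ (delivery day − start day).

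Worked examples, 30-day visits and delivery at 40 weeks (day 280):
- Start at 20 weeks: 280 − 140 = 140 days; 4 × 30 = 120; gap 20 days; 20/140 = 14%. Last visit at 20 + 120/7 = 37.1 weeks.
- Start at 24 weeks: 280 − 168 = 112 days; 3 × 30 = 90; gap 22 days; 22/112 = 20%. Last visit at 24 + 90/7 = 36.9 weeks.
- Start at 28 weeks: 280 − 196 = 84 days; 2 × 30 = 60; gap 24 days; 24/84 = 29%. Last visit at 28 + 60/7 = 36.6 weeks.

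Averaged over all start days, for each delivery week from 37 to 41:
- Mean gap: 13 to 15 days.
- Mean share of exposure: 0.115 to 0.166, that is 12-17%.
- Maximum gap: 27 days with 28-day visits, 29 days with 30-day visits.
- Maximum share: 0.24 to 0.33, depending on delivery week. The high end belongs to later starters, for example 29/89 = 0.33.

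A simulation with both start and delivery uniform over these ranges and 30-day visits gave a mean gap of 15.0 days and a mean share of 0.148, in agreement.

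**4. Women who leave.** 0.30 × 372 = 111.6, about 112 women (about 56 per arm if equally split). Cause is not stated, so the number leaving because of side effects is anywhere from 0 to about 112.

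**The case against.** The strongest reply is that the plan has a reporting net beyond the monthly form. Women are told to report all adverse events at once, serious events have their own deadline, and postpartum and neonatal data are collected. A reader might infer from the visit schedule that late side effects, and those of women who leave, go unrecorded. The documents do not support that: these routes would catch some of them. What remains is that non-serious events such as rash, nausea or diarrhea are not asked about after the last visit. The reminder to report sits on the questionnaire itself, so a woman who no longer attends no longer receives it. The postpartum data are not described as covering capsule tolerability or compliance.

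A second inference would be that a woman who stops capsules misses her next visit, so that rates come only from women who tolerated them. Nothing says so. Study visits take place at prenatal appointments, stopping capsules is not stated to end them, and a woman who leaves still contributes every form completed beforehand. She may miss the next visit; the plan does not say that she will.

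Third, 112 should not be read as the number of women with an unassessed interval. Some may leave at a visit, and the timing is not given. It is an upper bound.

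Three further points stand as limits. Side effects are monitored items, not primary or secondary outcomes, and no comparison by arm is specified for them. The unseen Appendix B may ask why capsules were missed or stopped, though as a form for monthly visits it would not reach women who have left. In the worked examples the last visit falls at 36.6 to 37.1 weeks, so the unmeasured compliance interval lies largely after the 35-37 week culture and bears little on the primary outcome.

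**Conclusion.** The point holds as a modest gap in active data collection. Solicitation of side effects and measurement of compliance end at the last monthly prenatal visit, while exposure continues to delivery, and there is no exit assessment. The unassessed interval averages about 2 weeks, 12-17% of exposure, and is at most 27-29 days. These figures rest on the assumed visit spacing and delivery weeks, and they are shares of exposure time, not of events. The size of any bias in side-effect rates by arm cannot be computed from the documents, because neither the reasons for leaving nor the tolerability by arm is given. The gap does not undermine the primary analysis, and it does not extend to serious events or to postpartum and neonatal outcomes.

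**What to change.** Amend Clinical Protocol items 8, 9 and 13 as follows:
- Repeat the existing questionnaire and capsule count once, at delivery or the routine postpartum contact, covering the time since the last visit.
- When a woman stops capsules or withdraws and can be reached, complete the same form then, by telephone if necessary, and record her reason for stopping.
- State that delivery and neonatal data are taken from the record for every randomised woman who has not withdrawn consent, including those off capsules and those delivering preterm, in line with intention to treat.

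This reuses an existing form, largely at a point where data are already collected. It changes neither the sample size nor the treatment. The cost is minor coordinator time. Women truly lost to follow-up will still be missed, so reports should give the number without a final assessment in each arm.

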Review of the literature does not demonstrate any specific strains of probiotic organisms that are known to be effective in displacing GBS either in the gut or in the reproductive tract and no study has investigated whether probiotics may effect rectovaginal colonization in pregnant women. However, the biological plausibility exists that there may be a beneficial effect of decreased GBS colonization given observed associations of reduction of other genital infections with probiotic therapy.

Preliminary Studies

In an empiric observational case series in two midwifery practices, 80 pregnant women were supplemented with oral probiotics. Given the average colonization rates, we would expect 10-30% GBS colonization rate or 8-24 cases in this cohort. However, of the 80 women who took oral probiotics throughout their pregnancies, only 1 woman had GBS

colonization (1.25%) at time of screening between 35-37 weeks. (personal communication)

Methods

A. Design: prospective randomized double-blind placebo-controlled trial.

B. Site: A collaborative trial including Stanford University School of Medicine/Lucile Packard Children's Hospital (LPCH) Obstetric Clinic, Dominican Hospital/ Aptos Women's Health (AWH) private Obstetrics-Gynecology practice in Santa Cruz, and private Midwifery Practice of [name], a certified midwife and co-investigator of this study. We plan to enroll the majority of subjects (approximately 2/3) at Stanford University School of Medicine/Lucile Packard Children's Hospital Obstetric Clinic.

C. Inclusion criteria:

1. Pregnant women < 28 weeks' gestation.
2. 18 years of age or older.
3. Singleton gestation.

D. Exclusion criteria:

1. Preexisting morbidity: Immunocompromised status (HIV +; malignancy; history of organ transplant; chronic steroid therapy; autoimmune disease requiring treatment during pregnancy, and other immunocompromised states); Type 1 diabetes and type 2 diabetes; congenital cardiac disease and cardiac valvular disease requiring antibiotic prophylaxis during procedure/labor; pulmonary disease (except mild asthma); renal disease; chronic hepatic disease (Hepatitis B, C); inflammatory bowel disease (Crohn's disease or ulcerative colitis); stomach or duodenal ulcer; bowel resection, gastric bypass, and chronic indwelling venous, bladder, or gastric catheter.
2. Multi-fetal gestation.

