Oral Probiotic Supplementation and Group B Streptococcus Rectovaginal Colonization in Pregnant Women: a Randomized Double-blind Placebo-controlled Trial

NCT01479478

July 14, 2017

[name], Principal Investigator
Stanford University
Stanford, California 94305

Statistical analysis plan

Treatment group characteristics will be summarized and reported using numbers and percentages for categorical data, means and standard deviation for normally distributed data, and medians and interquartile ranges (IQR) for non-normally distributed data. Characteristics will be compared between the treatment groups using the standardized mean difference.

Binary study outcomes will be compared between treatment groups using the Cochran-Mantel-Haenszel test. Normally distributed outcomes will be compared using linear regression adjusting for site. Non-normally distributed outcomes will be compared using the van Elteren (vE) test; a stratified Wilcoxon-Mann-Whitney test. In all cases treatment effects, 95% confidence intervals and p-values will be reported. All analyses will be performed according to intention-to-treat. P-values $\leq .05$ will be considered significant. All statistical analysis was performed using SAS 9.4.

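### The sample size of 133 per arm gives about 53% power for 25% versus 15%, not the stated 80%; a two-arm comparison needs about 250 evaluable women per arm

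*Protocol*

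**What the plan says.** The calculation is in the Protocol, Methods, G. Sample size calculation.

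- **Control rate (item 1).** "The baseline rectovaginal GBS colonization is approximately 25% in recent years in our practice".
- **Target effect (item 1).** "we have powered the study to identify a 40% reduction of GBS colonization to 15" percent.
- **Size and power (item 1).** "Using a two-tailed alpha of 0.05, 133 patients per arm (266 patients total) are needed to fulfill a power of 80" percent.
- **Expected loss (item 2).** "Given anticipated 30% drop out/lost to follow-up and 10% preterm delivery prior to 35-37 weeks' gestation". The protocol answers this by raising the size by 40%.
- **Recruitment (item 2).** "Therefore, we propose recruitment of 372 patients total (186 in each arm").

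The design is stated under Methods, item A: "A. Design: prospective randomized double-blind placebo-controlled trial". Specific aim 1 compares the colonization rate with the rate under placebo. H. Statistics names the uncorrected chi-square or Fisher exact test for categorical data. The SAP replaces this with a stratified test: "Binary study outcomes will be compared between treatment groups using the Cochran-Mantel-Haenszel test". It adds: "In all cases treatment effects, 95% confidence intervals and p-values will be reported".

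**The concern.** Item 1 gives every input needed to check the number, and 133 per arm is far below what a comparison of 25% with 15% usually requires. This is the only justification of sample size for the primary outcome, and the recruitment total of 372 is built on it.

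If the power is overstated, a null result will be misread. A reader who trusts 80% power would take a non-significant difference as fair evidence against a 40% reduction. At the true power, such a result would be nearly as likely as not even if that reduction were real.

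**Working it through.** **Inputs.** Control rate p1 = 0.25, probiotic rate p2 = 0.15, two-sided alpha 0.05 (z = 1.960), power 80% (z = 0.8416), equal allocation (all from G. Sample size calculation). The mean rate is 0.20, so:

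- 2 × 0.20 × 0.80 = 0.32
- 0.25 × 0.75 + 0.15 × 0.85 = 0.1875 + 0.1275 = 0.315

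**Step 1: try to reproduce 133.** Two-sample formula with pooled variance under the null:

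n = (1.960 × √0.32 + 0.8416 × √0.315)² / 0.10² = (1.1087 + 0.4724)² / 0.01 = 249.98, so **250 per arm**

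Other versions at 80% power:

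| Method | n per arm |
|---|---|
| Unpooled variance | 247.2 → 248 |
| Continuity-corrected | 269.6 → 270 |
| One-sided 0.05 | 196.8 → 197 |
| **One-sample test of 15% against a fixed 25%** | **132.07 → 133** |

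Only the last row gives the protocol's figure: (1.960 × √0.1875 + 0.8416 × √0.1275)² / 0.01 = (0.8487 + 0.3005)² / 0.01 = 132.07. That calculation treats the placebo rate as known and ignores its sampling error. It does not fit a trial that estimates the rate in both arms.

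Nor can 266 be read as a per-arm number. The text labels it a total, and 266 × 1.4 = 372.4, which is the recruitment total split as 186 per arm.

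**Step 2: power at the numbers the plan could yield.**

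Power(n) = Φ[(0.10 − 1.960 × √(0.32/n)) / √(0.315/n)]

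At n = 133: (0.10 − 1.960 × 0.04905) / 0.04867 = 0.079, and Φ(0.079) = 0.532.

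| Evaluable per arm | Where it comes from | Power, normal approximation | Power, exact (uncorrected chi-square) |
|---|---|---|---|
| 112 | 186 × 0.60 = 111.6 | 46.4% | 46.6% |
| 133 | Item 1 | 53.2% | 53.7% |
| 186 | No loss at all | 67.5% | 67.7% |
| 250 | Two-sample requirement | 80.0% | 80.3% |

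**Step 3: the effect detectable with 80% power, starting from 25%.**

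| Evaluable per arm | Probiotic rate | Relative reduction |
|---|---|---|
| 112 | about 10.7% | 57% |
| 133 | about 11.8% | 53% |
| 186 | about 13.6% | 46% |

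In none of these cases does the detectable effect come down to the 40% reduction the protocol names.

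**The case against.** The central arithmetic cannot be rescued, but several points limit how it should be stated.

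- **250 is specific to one method.** Two-sided versions run from 248 to 270, and H. Statistics also allows Fisher's test, under which power at 133 per arm is about 48%. This stands, and none of it helps the protocol.
- **The 46% figure is conditional.** It assumes that the 30% and 10% losses add. If they act in sequence, 186 × 0.70 × 0.90 leaves about 117 per arm and power of about 48%. I. Clinical Protocol, item 7, also plans cultures for some women who deliver preterm, and it is unclear whether these count toward an outcome defined at 35-37 weeks. So 46% should be labelled as the additive-loss case. The finding at 133 and at 186 does not depend on it.
- **Site stratification might add power.** The documents give no site-specific rates, so the effect cannot be computed. To reach 80% at 133 per arm it would have to stand in for nearly half of the 250 required, which is unlikely.
- **The SAP already promises confidence intervals.** This lessens the risk of misreading a null result, but the protocol still claims a power it does not have.

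**Conclusion.** The stated power is wrong for this design. With 133 evaluable women per arm, the trial has about 53% power to detect 25% versus 15% at two-sided 0.05, and it would miss that effect about 47% of the time. For 80% power it needs about 250 evaluable per arm, 1.88 times the stated number (250 / 133). No level of follow-up within the planned 186 per arm reaches 80%.

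These figures take the protocol's 25% and 15% as given, an unstratified comparison, and the full 0.05 at the final analysis. I. Data safety and monitoring plans schedules an interim analysis at 150 subjects with no stated alpha rule; any alpha spent there would tend to lower the final power. The one-sample origin of 133 is an inference, and the conclusion does not rest on it.

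**What to change.** Keep the recruitment target and correct the text.

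1. **Item 1.** Replace the 80% claim with the power for 25% versus 15% by evaluable number: about 46% at 112 per arm, 53% at 133 and 67.5% at 186. Alternatively, state the effect detectable with 80% power at 133 per arm: 25% to about 11.8%, a relative reduction of about 53%. Say that 80% power for 25% versus 15% would need about 250 evaluable per arm.
2. **Item 2.** Present 372 as the planned recruitment, since it no longer follows from an 80% power target.
3. **Interpretation.** State that a non-significant primary result will be read from the 95% confidence interval the SAP already requires, and not as evidence against a 40% reduction.

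The cost is a change of wording and a less favourable stated power. It needs no added participants, product or visits, and can be made at any stage of the trial. Enrolling up to 80% power is not proposed: with a 40% loss it would take 250 / 0.60 = 417 per arm (834 in total), or 250 / (0.70 × 0.90) = 397 per arm if the losses act in sequence, against 186 per arm planned.

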3. Regular use of probiotics preparations in the 3 months prior to beginning the study treatment or use of any additional probiotics preparations (other than study treatment) at any time during the study period (including over the counter food supplements such as Activia, BioK, other oral or vaginal probiotics products (BUT not including other common forms of yogurt).
4. Chronic (daily) use of broad spectrum antibiotics.
5. History of infant with GBS sepsis.
6. IUGR, Fetal Anomalies-major diagnosed at time of second trimester anatomy ultrasound
7. Anticipated delivery <35 weeks for maternal/fetal indication
8. Placenta previa or accreta (with anticipated delivery prior to 35 weeks)

E. Outcomes:

1. **Primary:** GBS colonization at 35-37 weeks

2. Secondary: maternal ante- intra- and postpartum outcomes (urinary tract infections, chorioamnionitis, endometritis, cellulitis, bacteremia, sepsis, and other infectious morbidity) and neonatal outcomes (gestational age at delivery, APGAR scores, bilirubin levels, C-reactive protein, rule out sepsis evaluation, sepsis, pneumonia, meningitis, neonatal ICU admission, and length of hospital stay).

F. Agents:

1. Treatment arm: Study probiotic dietary supplement arm will consist of 1 capsule (>1 billion CFU/capsule) daily including two strains, Lactobacillus rhamnosus GR-1 and Lactobacillus reuteri RC-14, which have been shown to reduce the incidence of bacterial vaginosis and candidiasis. (43) Those two strains are present in Jarrow's Femdophilus, which is produced by Chr Hansen in Denmark under the brand name Urex. Shelf life is two years when stored at room temperature (max 25 degrees Celsius).

2. Control arm: Placebo arm will consist of one inert (heat inactivated) capsule daily.

G. Study Drug and Placebo Supply, Transport, and Storage:

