1. Chr Hansen A/S will provide the active probiotic dietary supplement and placebo oral tablets for 372 patients (186 per arm of the trial.) However, the company providing the study probiotic dietary supplement and placebo will not have access to preliminary data during the conduct of the study and will not have the right of review of the results prior to publication. In summary, 27,900 doses of product and 27,900 doses of placebo will be provided. (Appendix 1) Capsules will be packed in aluminum tubes and these will then be packed in cardboard boxes and sent by courier from manufacturer to study site. The tubes containing the capsules will be packed such that no physical damage will occur to the individual capsules. Refrigeration is not necessary since bacteria count of minimum 1 billion is guaranteed for 2 years when stored at room temperature up to 25 degrees Celsius. Capsules should not be exposed to direct sunlight when stored. The manufacturer recommends 5 degrees Celsius storage to preserve bacterial potency if more than 6 months of storage is expected. Study participants will be instructed to store capsules outside of children's reach and at room temperature and to avoid direct sun exposure to capsules.

H. Patient Recruitment:

1. Pregnant study subjects who meet inclusion criteria will be recruited prior to 28 weeks' gestational age at one of the following collaborative sites by either study co-investigator or study staff: LPCH Obstetrics Clinic and the collaborating sites of AWH Obstetrics and Gynecology Clinic, other private obstetric-gynecology offices in Santa Cruz, and

homes of patients who have elected to receive prenatal care and delivery at home by Midwife [name], one of the co-investigators of this study.

I. Randomization Strategy:

1. Manufacturer will send identical probiotic and placebo capsules. The probiotic and placebo capsules will be originally packed in separate containers, labeled as designated probiotic versus placebo for each specific study enrollee (with study material information only available to the designated pharmacist at LPCH). The designated pharmacist at LPCH will be responsible for randomization assignment based on our pre-generated randomization table and distribution of study material to research coordinator for disbursement to enrollees at all sites.
 - a. Investigators will receive individual DEIDENTIFIED study material (patient probiotic versus placebo tubes) coded by a unique random number.

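### The 40% inflation is applied the wrong way round: 372 randomised women yield about 223 to 234 evaluable, 32 to 43 short of the 266 the protocol requires

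*Protocol*

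**What the plan says.** Protocol, Sample size calculation, item 1, works from 25% colonization without treatment and 15% with it. It states: "Using a two-tailed alpha of 0.05", 133 women per arm (266 in all) "are needed to fulfill a power of 80" percent.

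Item 2 then allows for losses: "Given anticipated 30% drop out/lost to follow-up and 10% preterm delivery prior to 35-37" weeks. It treats both as loss of subjects and continues: "we propose increasing our sample size by 40% to account for this subject loss". The result follows: "Therefore, we propose recruitment of 372 patients total (186 in each arm").

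Three other places bear on the point:

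- Outcomes, item 1, defines the primary outcome as "GBS colonization at 35-37 weeks".
- Clinical Protocol, item 7, says: "We will obtain a culture prior to initiation of antibiotics in those women delivering preterm without known group B strep status". It does not say whether these results enter the primary analysis.
- Study Drug and Placebo Supply sizes the supply to the same 372 women: "27,900 doses of product and 27,900 doses of placebo will be provided".

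The SAP has no sample size and no method for missing primary outcomes.

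**The concern.** A 40% loss applies to the women who enrol, not to the number wanted at the end. Adding 40% to 266 and then losing 40% of the larger number does not return 266. If the protocol's loss rates are right, the trial is planned to miss the number it calls necessary, while a reader of item 2 would believe that losses had been covered. The recruitment target and the product supply both rest on this step. A null result could also be misread, because fewer women would carry the primary comparison than the plan claims.

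**Working it through.** **Inputs** (Protocol, Sample size calculation): 266 evaluable women needed; drop-out 30%; preterm delivery 10%; rates 25% and 15%; two-sided alpha 0.05.

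**Reproducing the plan's figure.** 266 × 1.40 = 372.4, or 133 × 1.40 = 186.2 per arm. This matches 372 and 186, so the inflation was a multiplication by (1 + loss).

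**Loss that 372 can absorb.** 1 − 266/372 = 0.285. This is below the 30% drop-out before any preterm delivery is counted.

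**Expected evaluable women out of 372**

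| Reading of the losses | Evaluable | Short of 266 |
|---|---|---|
| Added, as in item 2 (40%) | 372 × 0.60 = 223.2 | 42.8 (16.1%) |
| In sequence (1 − 0.70 × 0.90 = 37%) | 372 × 0.70 × 0.90 = 234.4 | 31.6 (11.9%) |
| Drop-out only, every preterm woman counted through her culture (30%) | 372 × 0.70 = 260.4 | 5.6 (2.1%) |

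The first two rows are about 112 and 117 women per arm.

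**Enrolment that would yield 266.** Added: 133/0.60 = 221.7, so 222 per arm (444). In sequence: 133/0.63 = 211.1, so 212 per arm (424).

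**Isolated effect on power.** For n per arm, the usual two-sample approximation is

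power = Φ{[0.10 × √n − 1.96 × √(2 × 0.20 × 0.80)] / √(0.25 × 0.75 + 0.15 × 0.85)}.

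Exact enumeration of the uncorrected chi-square test is shown beside it.

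| n per arm | Approximation | Exact |
|---|---|---|
| 133 | 0.532 | 0.537 |
| 117 | 0.481 | 0.486 |
| 112 | 0.464 | 0.466 |

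The inflation error therefore costs 5 to 7 points. With a 25% control rate, the treated rate detectable with 80% power moves from about 11.8% at 133 per arm to 11.0% at 117 and 10.7% at 112. The last two are relative reductions of 56% and 57%.

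**The base figure, kept separate.** The same approximation needs 250 per arm for 80% power, not 133. That is a different error, and none of the shortfalls above depend on it.

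**The case against.** The arithmetic is not in dispute. Three arguments limit its weight.

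*Some women counted as lost may still have a result.* The 35–37 week culture is routine care and the analysis is by intention to treat, so a woman who stops her capsules may still be cultured. If the preterm cultures also counted, about 6 of the 112 expected drop-outs (372 × 0.30 = 111.6) having a result would bring the total to 266. Without the preterm cultures and with losses in sequence, about 32 of the 100 drop-outs who do not deliver preterm (372 × 0.30 × 0.90 = 100.4) would be enough. This is a fair reason to ask which cultures count. It does not rescue item 2, which plans for all these women as lost. Nor does intention to treat supply a missing culture.

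*The base figure matters more.* This stands. Restoring 266 evaluable women would still give only about 53% power. The two errors are nevertheless independent: correcting the base to 500 but keeping the 40% increase would give 700 enrolled and 420 to 441 evaluable. Item 2 needs its own correction.

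*The effect is moderate.* This also stands, and the 5 to 7 points should be reported as such.

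**Conclusion.** The point holds. On the protocol's stated losses, 372 women yield about 223 (added) or 234 (in sequence) with a primary outcome, 43 or 32 fewer than the 266 required. Even if every preterm woman counted through her culture, the expected number is about 260, a trivial gap of 6. The conclusion assumes, as item 2 does, that drop-outs contribute no primary outcome. It takes 266 as the protocol's own requirement and does not endorse it. The effect on power of this error alone is moderate, but it is a plain arithmetic error in the recruitment target for the primary outcome.

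**What to change.** **Preferred: keep 372 and correct what is said about it.** In Sample size calculation, item 2, remove the claim that a 40% increase offsets the losses. State that 372 is expected to yield about 223 to 234 evaluable women, with about 46–48% power for 25% versus 15%, and 80% power only for a fall from 25% to about 11%. State whether losses are added or sequential, and whether preterm cultures and routine cultures in women who stopped capsules count toward the primary outcome. The cost is one corrected calculation and a less favourable stated power, with no added women or doses.

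**Alternative: keep 266 evaluable as the goal.** Divide by (1 − loss) and set the target at 444 (222 per arm), or 424 (212 per arm) with sequential losses, with supply to match. That is 72 or 52 more women. The supply section implies 27,900/186 = 150 doses per woman, so this adds at most about 72 × 150 = 10,800 or 52 × 150 = 7,800 doses; drop-outs would use fewer. Power would still be about 53%, so this option should not be taken without also revisiting item 1. With 250 per arm as the base, the same division gives about 834 (500/0.60) or 794 (500/0.63).
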